5.2. Exclusion criteria

Participants are excluded from the study if any of the following criteria apply:

5.2.1. Medical Conditions

- a) Known hypersensitivity or idiosyncratic reaction to albendazole or any excipients or any related drug or any substance.
- b) History or presence of any disease or condition which might compromise the haemopoietic, renal, hepatic, endocrine, pulmonary, central nervous, cardiovascular, immunological, dermatological, gastrointestinal or any other body system.

221030

TMF-16298784 Protocol Version No. 1.0

- c) Any history or presence of asthma (including aspirin induced asthma) or nasal polyp or NSAIDs induced urticaria.
- d) History or presence of seizure or psychiatric disorders.

5.2.2. Prior/Concomitant Therapy

a) Ingestion of a medication (prescribed medication & OTC medication, herbal remedies, cimetidine, praziquantel, dexamethasone, ritonavir, phenytoin, carbamazepine, phenobarbital) at any time in 14 days prior to dosing of period I and any vaccine (including COVID-19 vaccine) from 14 days prior to dosing of period I. In any such case participant selection will be at the discretion of the Principal Investigator.

5.2.3. Prior/Concurrent Clinical Study Experience

- a) Receipt of an intervention or participation in a drug research study within a period of 90 days prior to the first dose of study intervention **.
 - ** If intervention is received within 90 days where there is no blood loss except safety lab testing, participant can be included considering 10 half-lives duration of intervention received.

5.2.4. Diagnostic Assessments

- a) A positive hepatitis screen including hepatitis B surface antigen and/or HCV antibodies.
- b) A positive test result for HIV antibody (1 and/or 2).
- c) The presence of clinically significant abnormal laboratory values during screening.

5.2.5. Other Exclusion Criteria

- a) Difficulty in swallowing oral solid dosage form like tablet/capsule.
- b) A recent history of harmful use of alcohol (less than 2 years), i.e. alcohol consumption of more than 14 standard drinks per week for men and more than 7 standard drinks per week for women (a standard drink is defined as 360 ml of beer or 150 ml of wine or 45 ml of 40% distilled spirits, such as rum, whisky, brandy etc.) or consumption of alcohol or alcoholic products within 48 hours prior to dosing of period I.
- c) Smokers, or who have smoked within last 6 months prior to dosing of period I.
- d) Consumption of grapefruits or grapefruit products within a period of 72 hours prior to dosing of period I.
- e) Use of any recreational drugs or history of drug addiction or testing positive in prestudy drug screening.
- f) A history of difficulty in donating blood.
- g) Donation of blood (1 unit or 350 mL) within a period of 90 days prior to the first dose of study intervention.
- h) An unusual diet, for whatever reason (e.g. low-sodium), for 4 weeks prior to dosing of Period I. In any such case participant selection will be at the discretion of the Principal Investigator.
- i) Nursing mothers (females).

5.3. Lifestyle considerations

5.3.1. Meals and dietary restrictions

• All participants will be required to fast overnight for at least 10 hours prior to serving of high fat high calorie vegetarian breakfast, which they are required to consume completely within 30 minutes of serving the same. The kilo calories and fat content derived from the vegetarian meal menu used in this study is approximately 937.66 and 540 kcal respectively, which is comparable to the non-vegetarian high fat high calorie meal menu as recommended by USFDA (Section 10.7). Lunch will be provided 5 hours after dose administration in each period.

The dietician/trained study person should weigh the leftover food and calculate the calories if the participant has not consumed the high fat high calorie vegetarian breakfast completely.

A standardize meal will be served to the participants at appropriate times during their stay in the clinical facility. The contents of the meals served during each period at various time points will be identical. The participants will receive lunch at least 5 hours after dosing in each period and further meals will be served at appropriate intervals from then on, until checkout in each period. Information on the amount of meal consumed and the time taken for consuming the meal will be recorded in the source data forms. The actual time of meal distributions will also be recorded. In case meals and blood sample collection coincide, samples will be collected at schedule time only.

Note: In case any participant has any adverse event and requires any change in diet, it will be done after consultation with the Principal Investigator. It will not be considered a protocol deviation. This will however be documented.

• No water (except 240 ± 2 mL given with study intervention administration) will be allowed from 1 hour before to 2 hour after dose administration in each period. Prior to and thereafter, water will be allowed at all times.

Note: Non-compliance to above fasting/fed requirements and water restriction will be recorded as protocol deviation.

- All participants to abstain from grapefruit, grapefruit products for 72 hours prior to intervention administration in period I till last PK sample collection of period IV.
- All participants to abstain from an unusual diet, for whatever reason (e.g. low-sodium), for 4 weeks prior to dosing of period I and throughout the their participation in the study.

5.3.2. Caffeine, alcohol, and tobacco

- All participants to abstain from any Xanthine containing food or beverages (like tea, coffee, chocolates or cola drinks), tobacco, tobacco containing products (Gutkha, Pan/Pan masala or any other) for 24 hours prior to intervention administration in each period and throughout their stay in the clinical facility in each period.
- All participants to abstain from recreational products, alcohol or alcoholic products for 48 hours prior to study intervention administration in period I till last PK sample collection of period IV.

• Smoking for 6 months prior to dosing in period I till the completion of the study is prohibited and the participants have to abstain from the same.

5.3.3. Activity

Postural Restriction

- The study intervention will be administered to participants while in sitting posture.
- Participants will be in sitting or ambulatory posture for the first 4 hours post-dose in each period unless medically necessary due to adverse event or procedurally required or natural exigency, in such cases it would not be considered as protocol deviation. In case of adverse event appropriate position will be given to the participants.
- Thereafter, the participants will be allowed to engage only in normal activities while avoiding any strenuous physical activity.

5.3.4. Other restrictions

Not Applicable

5.4. Screen failures

Not Applicable

5.5. Criteria for temporarily delaying

Not Applicable

6. STUDY INTERVENTION(S) AND CONCOMITANT THERAPY

The definition of study intervention is provided in the table of definitions.

6.1. Study intervention(s) administered

Table 5 Study Intervention(s) Administered

Intervention Label	Test (T)	Reference (R)
Intervention Name	Albendazole tablets IP 400 mg	Albendazole 400 mg tablets
Intervention Description	Solid dosage form	Solid dosage form
Type	Drug	Drug
Dose Formulation	Tablet	Tablet
Unit Dose Strength(s)	400 mg	400 mg
Dosage Level(s)	single oral dose of 400 mg	single oral dose of 400 mg
Route of Administration	oral	oral
Use	active comparator	active comparator
IMP and NIMP/AxMP.	Study intervention	Study intervention
Sourcing	Provided by the sponsor	Provided by the sponsor
Packaging and Labeling	Study intervention will be provided in container. Each container will be	Study intervention will be provided in container. Each container will be labeled as

labeled as required per	required per country
country requirement.	requirement.

While great care is taken to ensure comparability between the 2 tablets, minor differences exist (Table 6).

Table 6 Differences between Test and Reference tablets

Parameters	Test	Reference	Conclusion
Weight target	1026 mg	1026.20 mg	Very Slight Difference in Target Weight
Weight action limit	984.96 - 1067.04 mg (1026 mg ±4%)	974.89 to 1077.51 mg ((1026 mg ±5%)	Action limit of Reference is 5% while that of Test is 4%
Weight operating limit	995.22 – 1056.78 mg (1026 mg ±3%)	1021.07 to 1031.33 mg (1026 mg ±0.5%)	Operating limit of Reference is 0.5% while that of Test is 3 %
Hardness	108 N - 210 N (11.0 to 21.4 Kg/cm ²)	≥ 110 N Target 140 N (131-153 N)	Lower Hardness Limit of Test is 108 N while for Reference is 110 N.
Thickness	6.70 to 7.30 mm	6.65 to 7.10 mm	Thickness Limits of Test is wider than that of Reference

It is the expectation that these differences will not affect absorption kinetics or bioavailability to any significant degree.

6.2. Preparation, handling, storage, and accountability

- The sponsor shall supply adequate number of dosage units of study intervention for dose administration and for retention purpose. The received study interventions will be verified for the sealed condition of packs and adequacy of label (i.e. product name, strength, number of dosage units, manufacturer, manufactured date (if available), lot number or batch number, expiry date/retest date, study number, investigator and storage condition).
- The investigator or designee must confirm appropriate conditions (e.g., temperature) have been maintained during transit for all study intervention received, and any discrepancies are reported and resolved before use of the study intervention.

- Only participants enrolled in the study may receive study intervention, and only authorized clinical site staff i.e. The Pharmacy custodian or their designated study personnel will receive the study interventions with COA. The study interventions will be transferred to the pharmacy, after labelling it for project number (as applicable), product type, quantity and date of receipt, batch number or lot number, manufacturing date, expiry date/retest date, for clinical study use only & storage conditions.
- All study intervention must be stored in a secure, environmentally controlled, and monitored (manual or automated) area in accordance with the labeled storage conditions with access limited to the authorized site staff.
- Note: Information related to manufactured by/for, marketed/distributed by, marketing authorization holder etc. are based on details provided by the sponsor and/or available literature at the time of protocol development. Exact details will be captured in the study interventions receipt and accountability form by the pharmacy while receiving the study interventions. The same details can be used in the clinical study report for accuracy and compliance purpose.
- The Pharmacy Custodian and Project Coordinator or their designated study personnel will dispense the required units of study interventions prior to each period. Two units of study interventions (One test study intervention and one reference study intervention) will be dispensed in addition to the required number and labelled accordingly in each period. These will be used in any situation such as dropping the study intervention's etc. The remaining units of study interventions will be kept in their original containers.
- The doses intended for administration to the participants will be transferred to the drug-dispensing containers as per randomization schedule and properly labelled for the intervention with strength, dose, product type, project number, participant number, period, 'For Clinical Trial Use Only', Lambda Therapeutic Research Ltd.
- The personnel involved in dispensing and verification of dispensed study interventions will be accountable for ensuring compliance to randomization schedule.
- The investigator, the pharmacy custodian/designate is responsible for study intervention accountability, reconciliation, and record maintenance (i.e., receipt, reconciliation, and final disposition records).
- Unused study interventions that have not been dispensed will be retained in their original containers. Any product that had been dispensed but not used (e.g. due to the participant being unwell or dropping out from the trial etc.) will be labelled as 'Not For Use' and returned to the pharmacy and will be retained along with the other study interventions of its type.
- Retention samples: Samples of the study intervention in the original container should be retained for possible confirmatory testing in the future in compliance with the applicable national requirements or international recommendations, as appropriate. Dispensed study intervention that were not administered should also be retained. All the study interventions not used during the study will be accounted for and all unused supplies will be retained for 5 years after study completion. Once the above-mentioned time period is over, samples will be returned to the sponsor or as per sponsor's request necessary action will be taken.

6.3. Assignment to study intervention

Randomization

The order of receiving test (T) and reference (R) intervention for each participant during all the periods of the study will be determined according to a randomization schedule by Lambda. The randomization schedule will be generated using SAS® Version 9.4 or higher (SAS Institute Inc., USA) by a biostatistician.

The sequence of administration of intervention i.e. "TRTR" or "RTRT" to the participants will be determined according to the randomization schedule. (Note: T = Test study intervention and R = Reference study intervention). Equal allocation of participants in each sequence is planned.

The personnel involved in dispensing of study intervention and verification of dispensed study interventions will be accountable for ensuring compliance to randomization schedule.

6.4. Blinding, masking

Not Applicable

6.5. Study intervention compliance

Dosing activity will be followed by thorough mouth check with torch & disposable spatula by the trained study personnel immediately after study intervention administration to access compliance to dosing. The time of administration of the study intervention will be the time at which the participant completes drinking 240 ± 2 mL of water and that will be captured in the respective source data forms.

6.6. Dose modification

Not Applicable

6.7. Continued access to study intervention after the end of the study

There is no intervention following the end of the study.

6.8. Treatment of overdose

Not Applicable.

6.9. Prior and concomitant therapy

No drug (prescribed & OTC medication including herbal remedies, cimetidine, praziquantel, dexamethasone, ritonavir, phenytoin, carbamazepine, phenobarbital) other than the intervention shall be consumed by the participants from 14 days prior to dosing of period I till completion of study and any vaccine (including COVID-19 vaccine) within 14 days prior to dosing of each period. If drug therapy other than that specified in the protocol is required prior to dosing or during the study or in the wash-out period, decisions shall be taken by the Principal Investigator to continue or discontinue the Participants based on the

TMF-16298784 following:

- a) The pharmacology and pharmacokinetic of the non-study medicine.
- b) The likelihood of a drug-drug interaction, thereby affecting the pharmacokinetic comparison of study intervention.
- c) The time and duration of administration of the non-study medicine.

All such instances will be recorded and reported in the final report.

Note: Any concomitant medication administered during the course of the trial will be documented appropriately in the source data forms.

6.9.1. Rescue medicine

Not Applicable.

7. DISCONTINUATION OF STUDY INTERVENTION AND PARTICIPANT DISCONTINUATION/WITHDRAWAL

7.1. Discontinuation of study intervention

Not Applicable

7.1.1. Liver chemistry stopping criteria

Discontinuation of study intervention in the best interest of the participant for abnormal liver tests at the investigator discretion, when liver parameter falls outside the pre-defined clinically acceptable values. Acceptable limits are defined in Section 10.6.

If any participant has clinically significant abnormal liver function analysis, in such case participant may be discontinued for specific period at the investigator discretion. The decision to continue/discontinue such participants will be based on investigator's decision and it will be appropriately documented in the eCRF.

7.1.2. QTc Stopping criteria

Not Applicable

7.1.3. Temporary discontinuation

Not Applicable

7.1.4. Rechallenge

Not Applicable

TMF-16298784 Protocol Version No. 1.0

7.1.4.1. Study Intervention Restart or Rechallenge After Liver Stopping Criteria Are Met

Study intervention restart or rechallenge after liver chemistry stopping criteria are met by any participant in this study are not allowed.

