2.3. Benefit/risk assessment

Participation in bioavailability studies yields no direct benefit to the participants. However, a charge-free study related health assessment is provided. The risks as described below are reduced considering the fact only 4 doses are to be administered at an interval of at least 7 days between dosing days of any 2 successive periods.

Table 3 Potential risks and risk mitigation strategies

The potential risks of clinical significance for albendazole tablets are derived from the prescribing information (Albendazole label). Most of these reported risks are uncommon, rare or very rare. The likelihood of these risks in a healthy population receiving a single dose is therefore expected to be low. For complete list of adverse reactions please refer the prescribing information mentioned above.

Potential Risk of Clinical Significance	Summary of Data/Rationale for Risk	Mitigation Strategy
	Study Intervention(s)	
Hepatotoxicity	In 2001, GSK routine monitoring of spontaneous ADRs identified an increased number of reports of elevated liver enzymes in patients receiving low dose albendazole and reports of hepatitis and jaundice in patients receiving high dose albendazole. Higher doses of albendazole are used to treat systemic helminth infections for longer periods compared to the low dose, short treatment durations required for intestinal helminth infections in the OTC environment. A cumulative review of hepatic events was conducted to further evaluate the nature of these events and to determine whether GSK's CSI adequately reflected these adverse events. Following the review of the available data, GSK concluded that there was sufficient evidence to suspect albendazole as causing hepatic events; with low dose albendazole causing	This study will not include participants with abnormal liver function test results (transaminases). Discontinuation of study intervention in the best interest of the participant for abnormal liver tests at the investigator discretion, when liver parameter falls outside the pre-defined clinically acceptable values. If any participant has clinically significant abnormal liver function analysis during the study, in such case participant may be discontinued for specific period at the investigator discretion. The decision to continue/discontinue such participants will be based on investigator's decision.

Protocol Version No. 1.0

Detential Diely of Clinian	Summaria of	Mitigation Stratogy		

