7.2. Participant discontinuation/withdrawal from the study

The Principal Investigator may withdraw a participant from a period or from the study for any of the following reasons:

A participant may withdraw from the study at any time at the participant's own request for any reason (or without providing any reason). (Note: If the participant does not wish to be withdrawn from particular period only or from the study permanently then participant can be allowed to continue their participation in subsequent periods as per investigator's discretion).

A participant may be withdrawn at any time at the discretion of the investigator for safety reasons, any participant found to hide important medical history, violation of this protocol (this would include pre-study directions regarding alcohol and drug use, fasting/fed or if the participant is non-compliant during the study or uncooperative with study procedures).

If it is felt in Principal Investigator's opinion that it is not in the participant's best interest to continue.

The participant suffers from significant inter-current illness or undergoes surgery during the course of the study, or the participant has any significant symptoms or signs during the course of the study.

Note: For any participant who is withdrawn from any period due to emesis (within 4 hours post-dose) or any adverse events the decision regarding participant's continuation for subsequent periods will be based on investigator's discretion.

Any participant who requires the use of an unacceptable concomitant medication (prescribed & OTC medication including herbal remedies, cimetidine, praziquantel, dexamethasone, ritonavir, phenytoin, carbamazepine, phenobarbital).

Any vaccine (including COVID-19 vaccine) within 14 days prior to dosing of each period. In any such case decisions shall be taken by the Principal Investigator to continue or discontinue the participant.

If any participant cross-participates in other drug trial or trial screening.

Found positive in serum pregnancy test (for female participants).

Any participant experiences emesis before reported 2 times median T_{max} (i.e. 2 x 2hour = 4hour) after dosing of the study intervention for a particular period, then participant will be withdrawn for that period only or from study as per investigator's discretion.

Protocol Version No. 1.0

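### Protocol 7.1.1, Table 3 and the 7.2 note allow a temporary stop after a significant liver abnormality, while 7.1.4.1 forbids any restart and 7.1.3 provides for no temporary stop

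*Protocol*

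**What the plan says.** These parts of the protocol bear on dosing after an abnormal liver test:

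- **Section 7.1.1 (Liver chemistry stopping criteria), first paragraph.** The investigator may discontinue study intervention "when liver parameter falls outside the pre-defined clinically acceptable values. Acceptable limits are defined in Section 10.6".
- **Section 7.1.1, second paragraph.** For a clinically significant abnormality the "participant may be discontinued for specific period at the investigator discretion". The closing sentence leaves the choice between continuing and stopping to the investigator.
- **Table 3 (Section 2.3), hepatotoxicity row.** The same rule appears as risk mitigation: "in such case participant may be discontinued for specific period at the investigator discretion".
- **Section 7.2, note.** For a participant withdrawn from a period because of early emesis "or any adverse events the decision regarding participant's continuation for subsequent periods will be based on investigator's discretion".
- **Section 7.1.4.1.** "Study intervention restart or rechallenge after liver chemistry stopping criteria are met by any participant in this study are not allowed".
- **Section 7.1.3.** Under the heading "7.1.3. Temporary discontinuation" the only entry is that it does not apply.

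Section 8.3.4 schedules AST, ALT and total bilirubin before check-in to periods II, III and IV. It also has clinically significant laboratory changes recorded as adverse events, which brings them under the 7.2 note. The SAP does not address liver stopping or restart.

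**The concern.** Each participant is due four single 400 mg doses, so continuing in the study means being dosed again. Suppose a clinically significant ALT comes back before period II. Under 7.1.1, Table 3 or 7.2 the investigator may hold the participant out and then resume. Under 7.1.4.1 the investigator may not. None of the three permissive passages refers to the ban.

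Hepatotoxicity is the first risk in Table 3, which states that low-dose albendazole causes liver enzyme elevation. The tests before periods II to IV are the scheduled check on this risk before the next dose. What is at stake is participant safety and consistent conduct: the same result could be handled in opposite ways, each with support in the protocol.

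**Working it through.** The point is textual, and the plan has no figure of its own to reproduce. The steps are to compare the rules, look for a passage that reconciles them, and count the doses that separate them.

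**Step 1: the rules side by side**

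| Place | Length of stop | May dosing resume? |
|---|---|---|
| 7.1.1, second paragraph; Table 3 | Limited in time, length not given | Implied by the time limit; investigator decides |
| 7.2 note | A period, or the study | Investigator decides, for any adverse event |
| 7.1.3 | No temporary stop provided for | – |
| 7.1.4.1 | – | No, for any participant |

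Whether the period in 7.1.1 is a study period or a length of time, the stop is temporary.

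**Step 2: does another passage reconcile them?**

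- Section 8.3.4 requires repeat testing of significant values. It governs follow-up, not dosing.
- Section 10.5, titled as liver safety actions, gives only test times.
- Section 8.3.7 (study stopping rules) is marked not applicable.
- Where a permanent stop is intended, the protocol says so. Table 3 and Section 8.4.5 bar any later dose after a pregnancy. Section 7.1.1 has no such sentence.

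**Step 3: doses at issue**

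Inputs: four periods with one 400 mg dose each (Sections 2.3 and 8); at least 7 days between dosing days (4.1); liver tests before period k, where k = 2, 3 or 4 (8.3.4). The hold length is an assumption, because the documents give none.

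- Permanent stop (7.1.4.1): 0 further doses.
- One-period hold: period k is skipped and periods k+1 to 4 are dosed, giving 4 − k doses.
- Shorter delay with no period lost: periods k to 4 are dosed, giving 5 − k doses. Section 4.1 sets a minimum interval and no maximum. No section sets out such a delay, so this is the upper end of the range.

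| Result found before | 7.1.4.1 | One-period hold | Shorter delay |
|---|---|---|---|
| Period II (k = 2) | 0 | 2 (800 mg) | 3 (1200 mg) |
| Period III (k = 3) | 0 | 1 (400 mg) | 2 (800 mg) |
| Period IV (k = 4) | 0 | 0 | 1 (400 mg) |

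Holds longer than one period give fewer doses, down to 0. The counts are the same in TRTR and RTRT. After a one-period hold the first re-dose comes at least 2 × 7 = 14 days after the last dose.

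Continuing without any stop, which the end of 7.1.1 also leaves open, is not counted as part of the conflict, because a restart presupposes a stop.

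**The case against.** The strongest reply is that the protocol never defines when the stopping criteria are met. They might be met only when the investigator discontinues under the first paragraph of 7.1.1. That stop would be final under 7.1.4.1, and the second paragraph would cover other cases. It is true that no definition is given. But on this reading a value merely out of range leads to the permanent stop and a clinically significant one to the temporary stop, which is the wrong way round. If instead the criteria are met only once a permanent stop has been decided, the ban has nothing left to forbid.

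A second reply is that a permission and a prohibition can both be obeyed: a site that heeds 7.1.4.1 simply does not re-dose. That is the safe course. It also makes every stop permanent and leaves the time limit in 7.1.1 and Table 3 without meaning.

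A reader might also infer more than the text supports:

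- *That the not-applicable entries at 7.1 and 7.1.4 are further contradictions.* The entry under "7.1.4. Rechallenge" agrees with the ban, and 7.1 is a parent heading with substantive text below it. Only 7.1.3 adds to the conflict.
- *That 7.1.1 permits re-dosing once a value returns to normal.* Section 7.1.1 does not mention normalisation. That appears only in 8.3.4, as a rule for repeat testing.
- *That the conflict arises at exactly two of the three pre-period tests.* That holds only for the assumed one-period hold. With a shorter delay it arises at all three.
- *That the comparison of Test with Reference is biased.* Nothing in the documents shows this.

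It also stands that Section 2.3 expects these risks to be unlikely in healthy participants, and that 7.2 lets the investigator withdraw anyone for safety at any time.

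**Conclusion.** The protocol is wrong as written. Section 7.1.1, Table 3 and the 7.2 note permit a temporary stop and continuation that 7.1.4.1 forbids and for which 7.1.3 makes no provision. No other text in the protocol or SAP settles which governs.

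Per affected participant, the gap is 0 to 3 further doses for a result before period II, 0 to 2 before period III and 0 to 1 before period IV, depending on an unstated hold length. How many participants would be affected cannot be estimated, because no event rate is given. The finding concerns safety and conduct, not the validity of the bioequivalence test. It should be corrected, and the direction is clear because the sponsor's own express rule is the ban.

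**What to change.** 1. In 7.1.1 and Table 3, delete the words that limit the stop to a specific period.
2. Add to 7.1.1: *Whenever the investigator discontinues study intervention for a liver test abnormality (a value outside the Section 10.6 limits or one judged clinically significant), the liver chemistry stopping criteria are met and discontinuation is permanent under Section 7.1.4.1.* The two conditions should be joined by *or*. Requiring both would narrow the protection that 7.1.4.1 gives now.
3. Add to the adverse-event note in 7.2: *except liver abnormalities leading to discontinuation under 7.1.1, for which 7.1.4.1 applies.*

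Section 7.1.3 can then stay as it is. The investigator still judges whether to stop, so continuing without a stop remains possible. Whether stopping should be mandatory at a threshold is the sponsor's medical decision.

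**Cost.** No tests, visits or participants are added. The intermediate option of a hold is lost, so an occasional participant will miss later periods. The plan already allows for this: Section 9.6 assumes 48 complete participants of 70, so 70 − 48 = 22 (22/70 = 31.4%) may have no data, with joint power of 90.3% or 93.7% in its two CV scenarios. The wording change needs a protocol amendment, with ethics committee and health authority approval under Section 10.1.1.
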